## **8 STATISTICAL CONSIDERATIONS**

### **8.1 Statistical Methods**

#### **8.1.1 Baseline Data**

Baseline and demographic characteristics will be summarized by standard descriptive summaries (e.g. means and standard deviations for continuous variables such as age and percentages for categorical variables such as gender). Non-parametric analyses will be used in situations where the variables are not normally distributed. Baseline comparisons will be performed to test if there is any residual unbalance between the treatment and the control groups on demographic and other influential clinical variables. ANOVA or nonparametric ANOVA will be used to test continuous variables such as AGE. Chi-square or Fisher's Exact test will be used to test categorical variables such as GENDER. If a covariate is unbalanced, it will be included in the regression model for the multivariable analysis as a control variable

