### 1.2 Findings from pre-clinical and clinical studies

Currently, there are limited data regarding the early start of anticoagulation therapy following embolic stroke.

In the review of our local stroke database from October 2011 until December 2013, we examined the records of 336 small to medium stroke patients admitted to Tampa General Hospital with an ischemic stroke secondary to atrial fibrillation. The average age in our study population was  $75.3 \pm 1.83$  years of age. Stroke risk was similar to other AF groups in the literature, possessing an average CHADS2 score of  $2.6 \pm 0.26$  on admission; average CHA2DS2-VASc score was  $4.4 \pm 0.4$ . Average hospital stay was  $9.8 \pm 1.49$  days. We observed a  $24.7\% \pm 6.2\%$  mortality rate in our population prior to discharge. In addition, stroke survivors had a 5.1% recurrent non-fatal stroke risk. Patients with disabling or fatal

strokes were of a more advanced age than those who survived without severe disability ( $78.0 \pm 1.96$  years vs  $69.7 \pm 3.50$  years,  $p < 0.001$ ). Our data indicate that the risk of fatal to recurrent stroke is approximately 25 % with standard treatment (initiating anticoagulation approximately seven to fourteen days after signs and symptoms) for this group of patients.

The HAEST trial indicated that low molecular weight heparin results in a reduction in mortality and disability when used early (30 hours post stroke) in the treatment of ischemic stroke; however, this benefit is offset by an increased risk of intracranial hemorrhage

The previous studies on novel anticoagulation (NOAC) excluded subjects with a stroke/TIA within seven or less days; however, these randomized trials consistently demonstrated a lower risk of intracranial bleed compared to traditional anticoagulants ( see table 2).

[figure not shown]
ARISTOTLE followed a limited number of subjects (44) who suffered a stroke/TIA, between 7 and 14 days prior to randomization to treatment with either Apixaban or warfarin. There was only 1 subject in the warfarin group who suffered a major bleed. There were no recurrent stroke or systemic embolism in any of the 44 patients.

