#### **8.1.2 Efficacy Analysis/Primary Aim**

For the main outcomes, the proportion of patients with any primary outcome (fatal stroke, recurrent ischemic stroke, transient ischemic attack) will be computed along with the 95% confidence interval for the differences in treatment arms.

The primary outcome is defined as any component of the composite primary outcome occurred within 30 and 180 days or otherwise had adequate follow-up. Logistic regression models will be fitted with the primary outcome as the dependent variable and the SUBGROUP: (1) Apixaban TIA: day 0-3; (2). Apixaban small stroke: day 3-5; (3). Apixaban medium stroke: day 7-9; (4) warfarin TIA: day 7±5; (5) warfarin small stroke: day 14±5; (6) warfarin medium stroke: day 14±5 as the primary independent variable. The overall treatment effect will be assessed by the ESTIMATE and LSMEANS of all the Apixaban groups to all the warfarin groups. Comparison between individual subgroups will be assessed by constructing different ESTIMATE. For example, (1) Apixaban TIA versus (5) warfarin Small stroke: day 14±5. These analyses will be implemented by using SAS 9.2 PROC LOGISTIC which has the ESTIMATE and the LSMEANS statements for the group comparisons. P<0.05 is used for the overall treatment effects. All other subsequent subgroup testing will be adjusted for multiple comparisons by using PROC PLM.

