**8.1.4 Potential Confounders**

Age and sex as well as a variety of clinical variables (e.g. CHADS2-VASc, CHA2DS2) that are risk factors for embolic stroke, and their associations with fatal or recurrent embolic stroke or hemorrhagic cerebral bleed will be examined. Other clinically relevant variables that are shown to differ between treatment regimens at enrollment will also be examined as potential confounders.

For missing data, both an intent-to-treat analysis (in which subjects are analyzed according to their randomized assignment) and a per-protocol analysis (in which subjects not treated according to their randomized assignment and/or with other major protocol violations are removed from this analysis) will be conducted. Sensitivity analyses to assess the effect of missing outcome data on the primary result will be conducted

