### 8.1.6 Randomization

Randomization of treatment was calculated in SAS 9.4 using a stratified, blocked PLAN procedure. For the 120 subjects to be randomized to either apixaban or warfarin, a random seed number was generated. Each subgroup of stroke type (small stroke, medium stroke and TIA) was randomized implementing block randomization using four blocks of 10. The treatment allocation was created by an unblinded statistician and given to the TGH research pharmacy. Blinded study envelopes are provided to study team members for randomization.

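### Adjustment covariates are picked by baseline tests between randomised arms, so the adjusted logistic model is not fixed in advance

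*Combined protocol and SAP*

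**What the plan says.** All references are to the combined protocol and SAP.

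- **8.1.1 Baseline Data** sets the test: "Baseline comparisons will be performed to test if there is any residual unbalance between the treatment and the control groups". For the method it says "ANOVA or nonparametric ANOVA will be used to test continuous variables such as AGE", with chi-square or Fisher's exact for categorical variables. It then sets the consequence: "If a covariate is unbalanced, it will be included in the regression model for the multivariable analysis as a control variable". It gives no significance level or other cut-off for imbalance, and no closed list of what is tested.
- **8.1.4 Potential Confounders** opens with "Age and sex as well as a variety of clinical variables", including stroke risk scores, whose associations with outcome are to be examined. It does not commit any of them to a model. It then echoes the imbalance rule: "Other clinically relevant variables that are shown to differ between treatment regimens at enrollment will also be examined as potential confounders".
- **8.1.2 Efficacy Analysis/Primary Aim** first gives event proportions with a 95% confidence interval for the difference between arms. It then says "Logistic regression models will be fitted with the primary outcome as the dependent variable and the SUBGROUP" variable as the main independent variable. SUBGROUP has six levels, arm by stroke type. No covariate is named.
- **8.1.6 Randomization** stratifies by stroke type only: "Each subgroup of stroke type (small stroke, medium stroke and TIA) was randomized implementing block randomization using four blocks of 10".
- **1.2 Findings** reports from the local database that patients with disabling or fatal "strokes were of a more advanced age than those who survived without severe disability": 78.0 against 69.7 years, p<0.001.

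**The concern.** In a properly randomised trial, baseline differences between arms arise by chance. A significance test of such a difference therefore does not say whether the variable deserves adjustment. What makes a covariate worth including is its relation to the outcome, and the rule in 8.1.1 does not select on that. It can add a variable with no bearing on outcome because it differed by luck, and leave out a strong predictor whose imbalance fell short of significance.

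Two things are at stake.

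- **The adjusted model is unknown until the data are seen.** In logistic regression, adding a prognostic covariate also changes which odds ratio is estimated, because the conditional and marginal odds ratios differ. The reported quantity thus depends on which tests came out positive. In an open-label trial with no threshold and no list, that leaves room for choice after the fact.
- **Precision.** Variables the plan itself treats as risk factors are used only if they happen to differ between arms.

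**Working it through.** The plan states no figure for covariate selection, so there is none to reproduce. The check has four parts.

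**1. Chance that the rule adds something.** For k independent tests at level 0.05, the probability of at least one positive is 1 − 0.95^k. The number of tests, their independence and the level are all assumed, because 8.1.1 gives none of them.

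| k | 1 − 0.95^k |
|---|---|
| 5 | 23% |
| 8 | 34% |
| 10 | 40% |
| 15 | 54% |
| 20 | 64% |

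Correlated variables (age is likely to track the stroke risk scores) would lower these figures.

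**2. What the rule misses.** With 120 patients there are 60 per arm. A two-sided 0.05 test flags a mean difference only above about 1.96 × √(2/60) = 0.36 SD. For two given prognostic covariates, the chance that at least one is flagged is 1 − 0.95² = 9.75%, so about 90% of trials would adjust for neither.

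**3. Effect on power and type I error.** A simulation used 3,000 trials per scenario, 120 patients allocated 1:1, and eight independent normal covariates. Two of the eight were prognostic, at an odds ratio of 1.65 or 2.23 per SD. Treatment was the only design term. The covariate number and strengths are assumptions. Entries are the percentage of trials significant at two-sided 0.05.

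| Control vs experimental risk | OR per SD | Unadjusted | Baseline-tested rule | Two pre-specified |
|---|---|---|---|---|
| 20% vs 20% | 1.65 | 5.0 | 4.9 | 5.2 |
| 20% vs 20% | 2.23 | 4.7 | 4.5 | 4.7 |
| 20% vs 8.7% (ratio 2.30) | 1.65 | 38.9 | 38.1 | 41.1 |
| 20% vs 8.7% (ratio 2.30) | 2.23 | 40.0 | 39.5 | 45.2 |
| 20% vs 6.7% (ratio 3.00) | 1.65 | 54.1 | 52.8 | 56.2 |
| 20% vs 6.7% (ratio 3.00) | 2.23 | 52.9 | 52.7 | 59.8 |
| 46% vs 20% (ratio 2.30) | 1.65 | 86.7 | 87.1 | 88.9 |
| 46% vs 20% (ratio 2.30) | 2.23 | 85.8 | 86.2 | 92.4 |

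Pre-specified adjustment gains about 2 to 7 points over the baseline-tested rule. The rule itself performs about like no adjustment (from −1.3 to +0.4 points). Type I error under the rule is 4.9% and 4.5%, against a simulation standard error of √(0.05 × 0.95/3000) = 0.4 points.

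**4. How many covariates the data can carry.** Section 8.1.5 gives about 20% risk with standard treatment and a detectable ratio of 2.30 at 80% power with 50 per group. With 20% as the control risk, a two-sided 0.05 test of two proportions gives 36% power at that ratio. The stated 80% is matched (79.9%) only with 20% as the experimental risk and 46% as the control risk. That is a separate issue, but it means the event count needs a range. At 60 per arm:

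- 20% vs 8.7% (20%/2.30): 12 + 5.2 = 17.2 events
- 20% in both arms: 12 + 12 = 24 events
- 46% vs 20%: 27.6 + 12 = 39.6 events

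The SUBGROUP model has 1 + 5 = 6 parameters, which gives 17.2/6 = 2.9, 24/6 = 4.0 or 39.6/6 = 6.6 events per parameter before any covariate. A main-effects model with treatment (1), stroke type (2), two covariates (2) and an intercept (1) also has 6. Adding two covariates to SUBGROUP makes 8, or 2.2, 3.0 and 5.0 events per parameter.

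**The case against.** The strongest reply is that the plan never calls the multivariable analysis primary. Section 8.1.2 leads with the difference in proportions and its confidence interval, which no covariate rule touches. A reader might infer from 8.1.1 that the trial's main result turns on baseline tests. The documents do not establish that. They leave the status of the adjusted model open, and that gap itself needs closing. This part of the reply stands.

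Three further points on that side also stand.

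- A reader might infer that data-driven selection inflates the false-positive rate. The simulation showed no such inflation.
- A reader might infer that all prognostic information is thrown away. Stroke type, the stratification factor, is always in the model through SUBGROUP.
- The 8.7% is not a rate the plan expects. It is a detectable rate obtained by division. The 20% covers fatal or recurrent stroke, and counting TIA as in 8.1.2 could add events.

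Other points stand only in part.

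- Section 8.1.4 does name age, sex and risk scores on prognostic grounds. But examining their associations is not the same as fixing them in a model.
- With open-label treatment and fixed blocks of 10, a baseline comparison could hint at predictable allocation. That is a reason to look at the baseline table, not to let it choose covariates.
- The age evidence in 1.2 concerns disabling or fatal stroke, not recurrence, so it bears on only part of the composite.
- This is a pilot, and with power near 40% at 20% vs 8.7% the covariate choice will not settle the result. Even so, 8.1.5 says its data are to feed larger studies, which favours an estimate whose definition is fixed.

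**Conclusion.** The concern holds in a limited form. Sections 8.1.1 and 8.1.4 state a rule, not merely an omission. Under that rule chance imbalance decides the adjusted form of the only regression model in the plan, and nothing elsewhere fixes the covariate set. The harm is an adjusted odds ratio not defined in advance, plus a modest loss of precision.

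The 40% and 64% figures rest on an assumed number of tests, independence and threshold. The 2 to 7 power points rest on assumed covariate strengths that the documents neither give nor contradict. The finding does not extend to the unadjusted difference in proportions or to type I error. It should be corrected, but it does not undermine the trial.

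**What to change.** - **8.1.1:** delete the baseline significance tests and the rule that brings unbalanced covariates into the model. Present baseline data by arm descriptively.
- **8.1.2:** state which analysis is primary. Pre-specify one adjusted model for the overall effect: treatment, stroke type, and at most one or two named baselines already collected (age, for example), included whatever the observed balance. Provide for a penalised likelihood, such as Firth's, if events are sparse.
- **8.1.2, subgroup contrasts:** keep the SUBGROUP model for the within-stratum comparisons, which a main-effects model cannot supply.
- **8.1.4:** align the text with the above. Any adjustment prompted by observed imbalance becomes a labelled sensitivity analysis.

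The change costs wording only and needs no new data. It has two limits: the small number of events allows only one or two covariates, and the adjusted odds ratio is conditional on them, so it should be reported beside the unadjusted difference in proportions.

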#### **8.1.2 Efficacy Analysis/Primary Aim**

For the main outcomes, the proportion of patients with any primary outcome (fatal stroke, recurrent ischemic stroke, transient ischemic attack) will be computed along with the 95% confidence interval for the differences in treatment arms.

The primary outcome is defined as any component of the composite primary outcome occurred within 30 and 180 days or otherwise had adequate follow-up. Logistic regression models will be fitted with the primary outcome as the dependent variable and the SUBGROUP: (1) Apixaban TIA: day 0-3; (2). Apixaban small stroke: day 3-5; (3). Apixaban medium stroke: day 7-9; (4) warfarin TIA: day 7±5; (5) warfarin small stroke: day 14±5; (6) warfarin medium stroke: day 14±5 as the primary independent variable. The overall treatment effect will be assessed by the ESTIMATE and LSMEANS of all the Apixaban groups to all the warfarin groups. Comparison between individual subgroups will be assessed by constructing different ESTIMATE. For example, (1) Apixaban TIA versus (5) warfarin Small stroke: day 14±5. These analyses will be implemented by using SAS 9.2 PROC LOGISTIC which has the ESTIMATE and the LSMEANS statements for the group comparisons. P<0.05 is used for the overall treatment effects. All other subsequent subgroup testing will be adjusted for multiple comparisons by using PROC PLM.

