### **3 STUDY OBJECTIVES**

#### **3.1 Research Hypothesis**

Early anticoagulation treatment regimen with Apixaban at 0-3 days after TIA, 3-5 days after small ischemic stroke and 7 to 9days after medium ischemic stroke for patients with atrial fibrillation will result in a decreased incidence for recurrent ischemic stroke and without significant increase in risk of intracranial hemorrhage compared to conventional treatment for TIA, small and medium sized strokes.

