#### **3.2 Primary Objective**

In patients with atrial fibrillation with recent cerebral ischemic symptoms (0-48 hours), to evaluate whether the treatment regimen with Apixaban (Three subgroups: TIA: day 0-3; small stroke: day 3-5; medium stroke: day 7-9) compared with standard of care treatment regimen with warfarin (Three subgroups: TIA: day 7±5; Small or medium stroke: day 14±5) reduces the composite endpoint of fatal stroke, recurrent ischemic stroke or TIA at 30 and 180 days. (See figure 1)

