#### 4 INVESTIGATIONAL PLAN

##### 4.1 General Schema of Study Design

This will be a multi-center, open label, randomized, active control, parallel-group pilot trial to examine the effect of initiation of APIXABAN at days 0-3 (TIA), days 3-5 (small stroke) and days 7-9 (medium stroke) to decrease fatal and/or recurrent stroke/TIA in 120 subjects who have suffered a recent (0 to 48 hours from symptoms) TIA, or small to medium ischemic stroke as defined by appendix 13.1 compared to standard of care warfarin treatment regimen. Subjects will be randomly assigned in a 1:1 ratio to one of two treatment arms (apixaban or warfarin). Subjects will be followed for a total of 180 days from screening through follow-up.

[figure not shown]

Figure 1

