### **7 STUDY ENDPOINTS AND EVALUATIONS**

#### **7.1 Primary Endpoint**

Endpoint data will start at randomization up to 180 days. These composite endpoints include:

- Fatal stroke
- Recurrent Ischemic stroke
- New hemorrhagic stroke

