**8.1.5 Sample Size and Power**

As a pilot, open-label study, this project is intended to generate data to be used in the development of future, larger studies. A total of 120 patients are expected to be available and eligible to participate in this study and up to 125 may be screened in order to yield 120 randomized participants.

Review of our database indicates the risk of fatal or recurrent stroke in patients with atrial fibrillation is approximately 20% with standard treatment . To calculate expected power in this study, this established risk was used as the basis for estimates that could be expected with this treatment if it is successful. Given the parameters of conducting a 2-sided test with alpha = .05, and equal allocation to treatment and control groups (50 patients per group), power calculations were conducted using various ratios of outcomes (i.e. fatal or recurrent stroke) in the control group compared to the experimental group. The following results were obtained:

Power	Detectable outcome Risk in control / Risk in experimental
80% power	2.30

90% power	2.52
99% power	3.00

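### The primary composite counts TIA in Sections 3.2 and 8.1.2, but Section 7.1 drops TIA and counts new hemorrhagic stroke; no section ranks day 30 against day 180

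*Combined protocol and SAP*

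**What the plan says.** **Components.** The objective in Section 3.2 is to test whether early apixaban "reduces the composite endpoint of fatal stroke, recurrent ischemic stroke or TIA at 30 and 180 days". The analysis in Section 8.1.2 uses the same three components: "the proportion of patients with any primary outcome (fatal stroke, recurrent ischemic stroke, transient ischemic attack) will be computed". The design overview in Section 4.1 also includes TIA: "to decrease fatal and/or recurrent stroke/TIA in 120 subjects". Section 7.1 opens with "Endpoint data will start at randomization up to 180 days. These composite endpoints include" and then lists fatal stroke, recurrent ischemic stroke and "New hemorrhagic stroke". TIA is not on that list.

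Two other sections use further wording. The efficacy half of the hypothesis in Section 3.1 names recurrent ischemic stroke alone: early treatment "will result in a decreased incidence for recurrent ischemic stroke and without significant increase in risk of intracranial hemorrhage". The power calculation in Section 8.1.5 rests on a review finding that "the risk of fatal or recurrent stroke in patients with atrial fibrillation is approximately 20% with standard treatment".

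**Timing.** Section 3.2 gives two time points. Section 8.1.2 defines the outcome as "any component of the composite primary outcome occurred within 30 and 180 days". Section 7.1 gives only a window ending at day 180.

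**Testing.** Section 8.1.2 sets P<0.05 for the overall treatment effect and adjusts only the subgroup comparisons for multiplicity.

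**The concern.** A primary endpoint has to tell the analyst, for every patient, whether an event occurred. Here the answer for two kinds of patient depends on which section is read, and the time point is left open as well. The same data can therefore give more than one primary result, all consistent with the plan.

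Three features make this more than untidy drafting.

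- The trial is open label, and Section 2.3 says the stroke adjudicators know the treatment arm. An endpoint choice left open could be made with results by arm in view.
- The two versions answer different questions. With TIA, the composite is essentially ischemic efficacy. With hemorrhagic stroke, it mixes benefit and harm, while intracranial hemorrhage is also a secondary endpoint (7.2) and the outcome of the safety aim (8.1.3).
- Section 2.3.2.2 counts some asymptomatic imaging findings as hemorrhagic stroke. The 7.1 version could therefore take in events seen only on the day-14 or end-of-study scan.

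**Working it through.** **1. The definitions side by side**

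| Section | Stroke death | Further ischemic stroke | TIA | Hemorrhagic stroke | Time |
|---|---|---|---|---|---|
| 3.2 objective | yes | yes | yes | not listed | 30 and 180 days |
| 8.1.2 analysis | yes | yes | yes | not listed | 30 and 180 days |
| 4.1 design | yes | yes (stroke type not stated) | yes | not stated | none |
| 7.1 endpoint | yes | yes | not listed | yes, if new | up to 180 days |
| 3.1 hypothesis | no | yes | no | separate safety limb | none |
| 8.1.5 power | yes | yes (stroke type not stated) | no | not stated | none |

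The decisive conflict is 7.1 against 3.2 and 8.1.2. It needs no arithmetic.

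**2. The plan's only related figure**

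Section 8.1.5 states 80% power for a control/experimental risk ratio of 2.30 with 50 per group. The check uses the pooled normal approximation: power = Φ{[|p1 − p2| − 1.96·√(2p̄(1−p̄)/n)] / √(p1(1−p1)/n + p2(1−p2)/n)}.

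- 20% as the control risk: p2 = 0.20/2.30 = 0.087, p̄ = 0.143. Power = Φ[(0.113 − 0.137)/0.069] = 36%.
- 20% as the experimental risk: control = 0.20 × 2.30 = 0.46, p̄ = 0.33. Power = Φ[(0.26 − 0.184)/0.090] = 80%.

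The stated 80% appears only in the second reading, which contradicts the text. That is a separate issue. It matters here only for choosing simulation inputs and for showing that power is low under the plan's stated control risk.

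**3. How many patients are classified differently**

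Let q be the risk of TIA only, and also of hemorrhage only, equal in both arms. This is an assumption, since the documents give no such rates for this population. Of 120 patients, 120 × 2q are events under one composite and not the other: 1.2 at q = 0.5%, 4.8 at 2% and 12 at 5%. Events common to both composites number about 60 × 0.20 = 12 on warfarin and 60 × 0.087 = 5.2 on apixaban.

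**4. How often the verdict changes**

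Setup: 200,000 simulated trials per scenario, 60 per arm (120 randomized 1:1), 20 per stratum per arm assumed, two-sided 0.05. The shared events (fatal or recurrent stroke) have risk 20% against 8.7%. Composite A adds TIA (3.2, 8.1.2); composite B adds hemorrhage (7.1). The planned six-group logistic contrast is a Wald test, and a fit with an empty cell is scored as non-significant. An arm-level chi-square is shown for comparison.

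| q | Verdicts differ, six-group | Verdicts differ, chi-square |
|---|---|---|
| 0.5% | 6.2% | 8.3% |
| 1% | 10.1% | 12.5% |
| 2% | 15.5% | 17.4% |
| 3% | 19.1% | 20.6% |
| 5% | 23.9% | 25.1% |

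Low anchor for hemorrhage from the table of pivotal trials in Section 1.1: 0.47% per year on warfarin × 180/365 = 0.23%. With TIA-only at 2% or 5%, verdicts differ in 11.1% or 18.8% (six-group) and 13.3% or 19.6% (chi-square).

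Each composite alone is significant in only 15-23% of runs (six-group) or 35-41% (chi-square). Empty cells affect 39% of fits per composite at q = 0.5%, falling to 16% at 5%.

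**5. If there is no effect (20% against 20%)**

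At least one composite is significant in 4.4% to 7.5% of trials (six-group) or 6.1% to 8.6% (chi-square) as q goes from 0.5% to 5%. No inflation of type I error across the two time points is claimed for the planned contrast; that part of the problem is ambiguity.

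**The case against.** **This is a pilot, and the statistical section names its components.** True, but Section 8.1.2 still specifies a test at P<0.05. Section 8.1.5 says the data are meant to support larger studies, and an event rate for an unsettled composite serves that purpose poorly. The section that disagrees is the primary endpoint section itself.

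**Some of the cited conflicts are weak.** This stands. Section 3.1 is a hypothesis and Section 8.1.5 reports a historical risk, so neither is a rival definition of equal weight. On timing, the window in 7.1 leans toward day 180, although nothing demotes day 30.

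**Overlap with the safety aim is not peculiar to 7.1.** Partly right. A fatal hemorrhage could count as a fatal stroke under either version, and counting an event in both efficacy and safety is not in itself an error. Section 7.1 widens the overlap to non-fatal and scan-only hemorrhages.

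**The simulation rests on assumed rates.** This also stands.

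- If apixaban also lowers TIA by the 2.30 ratio and hemorrhage by the ratio in the Section 1.1 table (0.24/0.47), the six-group range becomes about 4-25%.
- With 46% against 20%, the pair that reproduces the stated power, it is about 4-14%.
- In the main scenarios, roughly 30-40% of six-group disagreements involve an empty cell (up to about half with the low hemorrhage anchor).
- The 0.47% anchor does not match the protocol's wider definition, which includes imaging findings.

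These points limit the figures to illustration. They do not touch the contradiction in the text.

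**Conclusion.** The concern holds. The plan gives two incompatible primary composites and two unranked time points, and nothing in the documents reconciles them. This must be fixed before analysis: it is a contradiction in the current text, not a missing detail.

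The conclusion rests on the text alone. The size is illustrative: different verdicts in about 6-24% of trials with the planned contrast (8-25% with a chi-square) at 60 per arm, 20% against 8.7%, and TIA-only and hemorrhage-only risks assumed at 0.5-5% and equal across arms. Part of that reflects low power, and other plausible inputs move the range as shown above. The component conflict is the serious half; the time-point ambiguity is secondary.

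**What to change.** Before analysis, state one primary composite and one primary time point in identical words in Sections 3.1, 3.2, 4.1, 7.1 and 8.1.2. Test that endpoint once at two-sided 0.05. List the other composite and the other time point as secondary.

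The choice belongs to the sponsor. The components already in the objective and analysis sections are stroke death, further ischemic stroke and TIA. Counting them over 180 days from randomization would also fit the window in 7.1, although 3.2 names day 30 as well.

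Three further statements are needed:

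- whether a fatal hemorrhage counts as a fatal stroke;
- the starting point of the clock, because 7.1 counts from randomization while a note to the schedule of procedures ties the study day at screening to the day of the event;
- in 8.1.5, that the 20% refers to fatal or recurrent stroke and that any rate for the chosen composite is an assumption.

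The cost is wording in those sections and in 8.1.5. No new patient data are needed and the adjudication definitions do not change. The composite and time point not chosen lose primary status. If TIA is kept, the primary endpoint includes a component defined by transient symptoms without imaging damage (2.3.2.1), which is exposed to unblinded judgment; the protocol should acknowledge this.
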